## 20.2 Retraining and Feedback

All EMS agencies will receive periodic training in trial procedures. Retraining will focus on proper execution of research procedures and reporting of data. Where possible, retraining will occur before each crossover period and as required by the ROC Study Monitoring Committee.

In keeping with the pragmatic design of the trial, the trial will not prescribe the frequency, methods or modalities for training in airway management techniques. EMS agencies will provide airway management skills training using their existing practices.

EMS personnel will receive study performance feedback throughout the trial.

## 21. Guidance for Receiving Emergency Departments

The practices and procedures employed by receiving Emergency Departments will not be dictated by this trial. However, to each potential receiving ED we will provide information on best ED practices for managing EMS-placed airways. This information will include:

- **Overview of the Trial** – We will provide an overview of the rationale for the trial and the trial interventions. We will provide an overview of the LT airway and its function.
- **Best Practices for Confirming EMS ET Tube Placement** – Best practices for confirming EMS ET tube placement will be reviewed. Emphasis will be placed on a) the need for using multiple modalities for confirming ET tube placement, b) the use of waveform capnography as a preferred modality for confirming tube placement, c) the use of direct laryngoscopic revisualization when placement is uncertain. Emphasis will be placed on the preference of maintaining EMS ET tube use over emergent ED re-intubation.
- **Best Practices and Strategies for Managing EMS-Inserted LT Airways** – Best practices for confirming EMS LT airway placement will be reviewed. The guidelines will encourage

using of the EMS LT for ongoing resuscitation, with conversion to ETI deferred until ROSC. Strategies for LT conversion to ETI will be reviewed, including direct laryngoscopy and intubation, exchange of LT to ET tube over a bougie, exchange of LT to ET tube over an Aintree catheter, and cricothyroidotomy or tracheotomy.

## **22. Study Monitoring**

### **22.1 Study Monitoring Committee**

The study leadership will appoint a Study Monitoring Committee (SMC) to oversee EMS participation and performance in the trial. The SMC will include, at minimum, the PI, the lead co-investigators, select members of the DCC, select members of the trial workgroup, select PIs from participating sites, and select representatives of NIH. The SMC will work with the study leadership to develop criteria for EMS agencies to enter and remain in the enrollment phase of the trial. Based upon reports provided by the DCC, the SMC will monitor EMS agency enrollment performance on a bi-monthly basis.

The SMC will have the final authority to authorize EMS agency participation in and/or suspension from participation in the trial.

### **22.2 Data Safety and Monitoring Board**

ROC has an existing independent Data Safety and Monitoring Board (DSMB) that will monitor adverse events throughout the trial and review outcomes data for possible harm. The DSMB was appointed by NHLBI. The committee will review and approve the protocol before the study commences. In addition, the committee will approve an interim monitoring plan before study initiation and review the results of the interim analyses. Although the DSMB will make the final decision about the interim monitoring plan, we anticipate that the DSMB will evaluate treatment compliance and the rate of adverse events between the treatment and control arms at intervals to be determined by the DSMB, expected to be approximately semi-annually. The DSMB will also monitor primary, secondary and mechanistic study outcomes between the treatment and control groups including main effects and a priori subgroups as specified elsewhere in the protocol. The DSMB will advise the investigators if a change in the protocol is warranted based on this interim monitoring.

The DCC will forward DSMB reports to study investigators, the Institutional Review Board, and the sponsor in accordance with the 1996 guidance from OHRP regulations 46.101 (i), as is our current practice.

Clinical staff will report all potential adverse events to the coordinating center as soon as possible. These will be collected in both a structured (standard form) and open (describing any difficulties encountered) form. All potential adverse events will be reviewed as to treatment arm and further classified by: a) Severity (life-threatening, serious, non-serious); and b) Expected vs. Unexpected. Expected adverse events will be recorded as noted in the hospital discharge summary by each enrolling site, reported to overseeing agencies as required by federal regulations and local requirements, and reviewed periodically by our independent data safety monitoring board.

For suspected unexpected serious adverse reactions (SUSAR), the coordinating center will promptly notify the DSMB as well as appropriate regulatory agencies, site and sponsor. The coordinating

center will tabulate and report compliance, data quality, and non-serious adverse events on a regular basis.

The SMC will carry out recommendations provided by the DSMB.

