**Figure 9 - American Heart Association Algorithm for Adult Cardiac Life Support**  
ETI or LT insertion may typically occur at boxes 6 and 10, "Consider advanced airway." EMS agencies will follow local ACLS protocols.

---

advanced-level EMS personnel will perform airway management (ETI, LT or BVM) during resuscitation as guided by local protocol or practice.

Upon arriving upon the scene of a potentially eligible subject, treating EMS personnel will initiate resuscitation measures per local BLS and ACLS protocol. Patient assessment, initiation and style of chest compressions, rhythm assessment, shock delivery, intravenous line insertion, and drug administration will be performed according to local protocol and practices.

Simultaneously, EMS personnel will verify eligibility for the trial (i.e., satisfaction of inclusion criteria and absence of any exclusion criteria).

At the point where they are ready to perform advanced airway insertion, EMS personnel will select the airway management technique to which they have been randomized (ETI or LT). EMS personnel will perform ETI or LT insertion using techniques consistent with local protocol.

EMS personnel will verify successful and correct placement of the ET tube or LT according to local protocols. Customary methods for confirming tube placement including physical examination (chest rise), auscultation of chest for presence of breath sounds, auscultation of epigastrium for absence of gastric sounds, use of a bulb syringe detection, use of a colorimetric end-tidal carbon dioxide detector, and use of a waveform digital end-tidal carbon dioxide detector.

EMS personnel will secure airway device in place per local protocol. Standard methods for securing the ET tube and LT airway include adhesive tape, umbilical “twill” tape and commercial tube holders. Of note, the LT cannot be secured using an ET tube commercial tube holder; rescuers should use adhesive tube or a tube holder designed for the larger diameter of the LT.

After securing the airway device, EMS personnel will continue with standard resuscitation measures. Decisions for termination of resuscitation in the field or transporting to receiving Emergency Department are not dictated by this trial.

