### 14.3.2 Expected Adverse Events

The following are events commonly observed in patients who experience cardiac arrest or resuscitative efforts after its onset, or who receive airway management efforts, and may or may not be attributable to specific resuscitation therapies. These events will be monitored and reported but not considered as adverse events of the study intervention.

- **Unsuccessful EMS airway insertion.** This event includes unsuccessful EMS ETI or LT insertion efforts. This event does not include ED airway insertion efforts. This event will be determined from EMS records.
- **Multiple EMS airway insertion attempts.** This event includes 3 or more EMS attempts to perform ETI, or 3 or more EMS attempts to insert the LT. This event does not include ED airway management efforts. This event will be determined from EMS records.
- **Unrecognized EMS airway misplacement or dislodgement.** This event includes unrecognized EMS endotracheal tube placement in the esophagus or hypopharynx, or displacement of a correctly placed ET tube. Airway misplacement and dislodgements are difficult to differentiate; this trial will not differentiate these events. Airway misplacement/dislodgement events will be determined from EMS and ED records.

This event does not include right mainstem intubations. This event does not include instances where EMS personnel immediately recognize and correct ET tube misplacement. This event does not include ED airway misplacements.

Misplacement and dislodgement events are unique to ETI and do not apply to the LT.

- **Inadequate EMS ventilation.** This event includes instances where EMS personnel a) perceive that a successfully inserted airway device is resulting in inadequate ventilation and b) therefore opt to change to another airway management device or technique. Inadequate ventilation connotes a) inability to insufflate any oxygen (airway obstruction) or b) inadequate chest rise on insufflation. Potential reasons for inadequate ventilation may include device obstruction, misplacement, malfunction or cuff leak, among others.

Inadequate ventilation will be based upon EMS personnel assessment, and will be determined from EMS patient care records.

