- **Airway swelling or edema.** A described complication of the LT is the development of major tongue, pharyngeal or hypopharyngeal swelling, which may interfere with ventilation. While usually associated with instances of prolonged LT ventilation (several hours), some clinicians have reported the occurrence of this event during resuscitative efforts. This event

will be based upon EMS and ED personnel assessment and will be determined from EMS and ED patient care records. The timeframe for surveillance for this event will be limited to the earlier of a) replacement of the LT with an ET tube, or b) the first 24 hours of hospitalization. While generally associated with LT insertion, we will monitor the occurrence of airway swelling or edema regardless of inserted airway device.

- **Oropharyngeal or hypopharyngeal injury.** Advanced airway insertion may result in injury to the oropharynx and hypopharynx, including soft tissue lacerations, injury to teeth, and perforation of pharyngeal, hypopharyngeal or other anatomic structures, among others. This event will be determined by review of the discharge summary and ED physician records and will be limited to injuries identified during the first 24 hours of hospitalization.
- **Pneumothorax.** Airway insertion and ventilatory efforts may cause pulmonary barotrauma, resulting in pneumothorax. This event will be determined from radiology or ED physician interpretation of the first chest x-ray or computed tomography (CT) performed in the ED.
- **Pneumonia and aspiration pneumonitis.** Pneumonia and aspiration pneumonitis are known sequelae of cardiac arrest and airway management. This event will be defined as the presence of an infiltrate or consolidation as reported by radiology interpretation of chest x-rays or computed tomography (CT) performed during the first 72 hours of hospitalization.

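### Section 22.2 takes expected adverse events from the hospital discharge summary, while Section 14.3.2 takes seven of the eight from EMS, ED or radiology records; the two need reconciling

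*Combined protocol and SAP*

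**What the plan says.** Section 22.2 describes how adverse events reach the DSMB. Clinical staff first report all potential events to the coordinating center, on a structured form and an open one. These are reviewed by arm and classified by severity and as expected or unexpected. The section then gives a rule for the expected class as a whole: "Expected adverse events will be recorded as noted in the hospital discharge summary by each enrolling site". Those events go to the overseeing agencies and, periodically, to the DSMB. No other source is named for them, and 14.3.2 is not cross-referenced.

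Section 14.3.2 defines eight expected events and assigns each a source:

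- Unsuccessful insertion, and multiple insertion attempts: "This event will be determined from EMS records" (same rule for both).
- Unrecognized misplacement or dislodgement: "Airway misplacement/dislodgement events will be determined from EMS and ED records".
- Inadequate ventilation: "Inadequate ventilation will be based upon EMS personnel assessment, and will be determined from EMS patient care records".
- Airway swelling or edema: "will be based upon EMS and ED personnel assessment and will be determined from EMS and ED patient care records".
- Oropharyngeal or hypopharyngeal injury: "This event will be determined by review of the discharge summary and ED physician records".
- Pneumothorax, from early imaging: "This event will be determined from radiology or ED physician interpretation of the first chest x-ray or computed tomography (CT) performed in the ED".
- Aspiration pneumonitis and pneumonia: radiology reports from the first 72 hours of hospitalization.

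Section 12.4 leaves field termination to local practice: "Decisions for termination of resuscitation in the field or transporting to receiving Emergency Department are not dictated by this trial". It also allows ED staff to end the resuscitation. Section 19.1.2 lists the discharge summary as one hospital record among several, separate from ED documentation, radiology reports and the death note.

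**The concern.** A site cannot apply both rules. For most of the eight events they point to different documents, and the plan does not say which prevails.

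The choice matters because a discharge summary is a record of an inpatient stay. A patient pronounced dead in the field or the ED would not be expected to have one. Under the 22.2 sentence, a failed airway followed by early death is the kind of event most easily lost, and whether an event is captured depends on something that happens after randomization. If the share of patients with a summary differed between the arms, recorded rates could differ where true rates do not.

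The comparison has uses. Section 22.2 expects the DSMB to look at adverse event rates between arms, and 16.2 names safety outcomes by treatment group among the factors in a stopping decision. The Summary and 15.4 count adverse events among the secondary outcomes.

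**Working it through.** The plan states no figure on this point, so there is none to reproduce. The check is a comparison of the two sections, followed by an illustration.

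**Step 1: sources side by side**

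| Source in 14.3.2 | Events | Uses the discharge summary? |
|---|---|---|
| EMS records | unsuccessful insertion; multiple attempts; inadequate ventilation (3) | no |
| EMS and ED records | misplacement or dislodgement; airway swelling (2) | no |
| First chest x-ray or CT in the ED | pneumothorax (1) | no |
| Radiology, first 72 hours | pneumonia or pneumonitis (1) | no |
| Discharge summary and ED physician records | oropharyngeal or hypopharyngeal injury (1) | yes, in part |

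Seven of the eight do not use the summary (3 + 2 + 1 + 1), one uses it with another source, and none relies on it alone. Section 22.2 applies it to all eight.

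**Step 2: what the 22.2 rule could do to an arm comparison**

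Inputs from the plan: 1,306 patients per arm, baseline 72-hour survival 13.7%, design difference 4.5 percentage points (16.1). Assumptions, because the documents give none of these figures: the same true event risk in both arms, illustrated at 10%; the share of patients with a discharge summary; no source other than the summary; every event noted when a summary exists; and event risk unrelated to having a summary.

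Recorded events in an arm = 1,306 × risk × share with a summary. True events = 1,306 × 0.10 = 130.6 per arm. The spurious ratio is share₂ / share₁, so the event risk cancels.

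| Shares with a summary | Recorded events | Ratio |
|---|---|---|
| equal in both arms | equal | 1.0 |
| 30% vs 34.5% | 130.6 × 0.300 = 39.2; 130.6 × 0.345 = 45.1 | 0.345 / 0.300 = 1.15 |
| 13.7% vs 18.2% (shares set to survival) | 130.6 × 0.137 = 17.9; 130.6 × 0.182 = 23.8 | 0.182 / 0.137 = 1.33 |

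With the 4.5 points in the other direction, the ratios are 0.255 / 0.300 = 0.85 and 0.092 / 0.137 = 0.67. In each unequal case the arm with more summaries appears to have more harm, although true risk is the same.

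The third row is an extreme choice: it treats every patient who is admitted and then dies within 72 hours as having no summary. The illustration does not apply to misplacement or dislodgement, which 14.3.2 defines for ETI only.

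**The case against.** The strongest reply is that the data are collected anyway. Section 22.2 itself has all potential events reported and reviewed by arm, and that route does not depend on a discharge summary. Section 14.2.2 has EMS personnel report the sequence, success and number of insertion attempts for each subject. Section 19.1 provides for review of all EMS and hospital records, 20.1 includes adverse events in data-reporting training, and Appendix 3 requires fewer than 10% missing entries in the required EMS elements. Because 22.2 also has the DSMB monitor secondary outcomes by arm, failed insertion and multiple attempts should reach it as airway-course data in any case. A general monitoring paragraph may fairly be read as yielding to event-specific definitions.

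Most of this stands. It lowers the practical risk, but it does not reconcile the sections: the reporting sentences name no source, and the later sentence assigns the expected class to the summary.

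It also rules out several stronger readings that a reader might infer:

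- That 22.2 governs, so an event is recorded only if the patient is admitted. Nothing gives 22.2 precedence, and the parallel reporting is in the same paragraph.
- That the assigned strategy is known to affect admission. Its effect on outcome is what the trial tests.
- That the 90.6% of deaths within three days (14.1.1) measures deaths without a summary. It comes from a Pittsburgh cohort and is not a share dying in the field or ED; 12.5.6 expects most trial patients to be transported to an ED.
- That 1.33 is an estimate. It is one assumed scenario.

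**Conclusion.** The conflict is real and lies in current text. For seven of eight expected events, 22.2 names a source that 14.3.2 does not use. Followed as written, the 22.2 sentence would tend to miss expected events in patients who die in the field or the ED, within that data stream. It could distort the arm comparison if the share of patients with a summary differs by arm.

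The size is unknown, because the documents give no admission rate, no summary rate and no arm difference in either. On the assumptions stated in the working, the spurious ratio runs from 1.0 with equal shares, through 1.15, to 1.33 when the shares are set to the design survival rates. These figures show the mechanism and its direction; they do not predict what the DSMB would see. The documents do not support the conclusion that the DSMB's safety review would rest on the summary-based stream alone. The supportable conclusion is that the plan states two incompatible recording rules for a secondary outcome and should state one.

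**What to change.** In 22.2, replace the discharge-summary wording with a statement along these lines: expected adverse events are recorded from the event-specific sources in 14.3.2 for every enrolled patient, including those who die in the field or ED, and are reported to the DSMB by assigned arm, with all enrolled patients as the denominator for EMS-sourced events.

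Two limits should be noted beside it. Hospital-sourced events such as pneumonia will still depend on survival to hospital, whichever section is followed. Misplacement or dislodgement is defined for ETI only, so it gives no comparison between devices.

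The cost is one sentence. No new data source is needed, because 19.1 already provides for review of all EMS and hospital records.

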## **23. Regulatory Considerations**

### **23.1 Human Subjects**

Because of the unconscious nature of cardiac arrest victims and the time-critical nature of OHCA care, the trial will be carried out under “Exception from informed consent required for emergency research” (EFIC) rules outlined in by the guidance document “Waiver of Informed Consent Requirements in Certain Emergency Research” (Federal Register, Vol. 61, pp. 51531-51533, November 1, 1996 - <http://www.gpo.gov/fdsys/pkg/FR-1996-10-02/html/96-24968.htm>), OHRP “Basic HHS Policy for Protection of Human Research Subjects” (45 CFR 46.101(i) - <http://www.hhs.gov/ohrp/humansubjects/guidance/45cfr46.html#46.101>), and FDA regulations 21 CFR 50.24.

The use of EFIC is justified because the victims of OHCA are in a life-threatening situation, available OHCA treatments are unproven or unsatisfactory, and obtaining informed consent prior to enrollment is not feasible because of their unconscious and critically-ill state, and trial interventions must be administered before consent from the subjects' legally authorized representatives is feasible. Cardiac arrest is a short-lived illness, for which immediate interventions cannot be delayed without irreparable harm to the patient.

In conformance with EFIC rules, measures to protect the rights and welfare of subjects will include, at least; a) community consultation, b) public disclosure, c) independent data monitoring, and d) notification of a legally authorized representative or family members of a subject's enrollment in the trial, with opportunity to discontinue trial participation.

Additional details are provided in Appendix 4. Suggested notification documents are provided in Appendix 5.

### **23.2 Food and Drug Administration**

Based upon review of a formal application submitted by the study team, the FDA confirmed that the trial is *exempt* from FDA Investigational Device Exemption (IDE) regulations. (Communication from FDA to [name], January 8, 2015.)

#### **23.2.1 Technical and Regulatory Information for the ET Tube**

The ET tube is listed in the FDA Medical Devices Database under the device name “Tube, Tracheal (w/wo connector)” and is classified as Device Class 2.

### 23.2.2 Technical and Regulatory Information for the LT

Models of the King LT airway are listed in the FDA Medical Devices Database. (Table 6) The predicate device is “Airway, Oropharyngeal, Anesthesiology.” There is no 510(K) number for the King LTS-D model, as it is considered a minimal modification of the LT-D and LTS models. We expect that only disposable versions of the King LT will be used in this study.

Manufacturer	FDA 510(K) #	Models
KING SYSTEMS, CORP NOBLESVILLE, IN	K021634	KING LT, MODELS # KLT 100, KLT 101, KLT 102, KLT 103, KLT 104, KLT 105
	K033186	KING LT-D DISPOSABLE OROPHARYNGEAL AIRWAY, MODELS KLT 203, KLT 204 AND KLT 205
	K033189	KING LTS REUSABLE OROPHARYNGEAL AIRWAY WITH DRAIN/ /SUCTION CHANNEL, MODELS KLT 303, KLT 304 AND KLT 305

Table 6 – King LT Models and Corresponding FDA 510(K) Numbers

## **25. Appendix 1 – Summary of Protocol Amendments**

### **25.1 Version 4.2, December 10, 2014**

- Results of initial protocol development.
- Protocol version sent to FDA.

### **25.2 Version 5.0, February 19, 2015**

- Revisions made in response to DSMB comments
- Removal of duplicate inclusion/exclusion criteria
- Modification of EFIC references from FDA to OHRP rules.
- Approved by DSMB on March 4, 2015

